### **2.5.1.5 SINS score at 3 and 6 months**

All patients who have had their baseline SINS score and at least one follow-up SINS score (at either 3 and/or 6 months) assessed will be considered evaluable for the spinal instability analysis.

### **2.5.1.6 Overall survival**

Overall survival is defined as the time from randomization to date of death. For patients who are alive will be censored at the last known alive date.

## **2.5.2 Analysis of Key Parameters**

The comparison between treatment arms will be carried out using a two-sided test at an alpha level of 5% unless otherwise specified. All efficacy analyses will be presented by treatment arm. The CONSORT diagram will be included.

### **2.5.2.1 Complete pain response at 3-month post treatment**

Patients will be considered to achieve a complete pain response if they meet the criteria for complete pain response outlined in 2.5.1.1.

A table of number of patients who were not evaluable for the primary endpoint of complete pain response will be provided by treatment arm. (Table 11).

A table of number of patients meeting the primary endpoint of complete pain response at 3-month after treatment start by arm will be provided. (Table 12).

The complete pain response rate is defined as number of patients achieved complete pain response / number of patients randomized for each treatment arm. Chi-square analysis will be applied to test the complete pain response rate between the two arms and the 95% confidence interval of the rate difference (SBRT arm – CRT arm) between the two arms will be calculated. The Cochran-Mantel-Hanzeal Chi-square will be used to test the difference in the complete pain response rate stratified by stratification factors at randomization except of study center. P-value from Chi-square test without adjustment for the stratification factors will also be provided for sensitivity.

Logistic regression will be used to assess the relationship between complete pain response incidence and the following factors (Table 13):

- Treatment arm
- Age (as a continuous variable and/or as a categorical variable: below and above median);
- Gender
- Primary Malignancy
- ECOG performance status
- Worst pain score at baseline
- SINS score.

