14.2 Primary Endpoints and Analysis

The primary endpoint of the phase II study is feasibility which is defined as the ability to accrue 54 patients over an 18 month period to a study that randomizes patients with spinal metastases to Stereotactic Body Radiotherapy (SBRT) or Standard Conventional Radiotherapy (CRT) within a Canadian multicentre setting.

The primary endpoint of the phase III study is the complete pain response at 3 months post-radiation, which is defined as in section 10.2.1. The analysis of the primary outcome will be based on the intent-to-treat principle, which will include all randomized patients, regardless of whether radiation therapy is given, given as per protocol, or whether there has been fidelity to treatment allocation. Patients that are inevaluable for the primary endpoint due to missing data will be considered as non-responder for the intent-to-treat analysis of the primary endpoint. The primary test will be the Cochran-Mantel-Hanzeal test stratified by baseline stratification factors of Histology (radioresistant vs. radiosensitive) and “Mass” on imaging (present vs. absent), a Chi-square analysis will also be applied to test the complete pain response rates between the two arms, and the 95% confidence limits of the rate difference between the two arms will be evaluated. Logistic regression will be used to estimate the treatment effect while adjusting for unbalanced important factors and to explore factors that are predictive of the complete pain response.

AMEND #1: 2017-FEB-02; AMEND #2: 2018-APR-03; AMEND #3: 2018-OCT-31

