14.3 Sample Size and Duration of Study

For the randomized phase II portion of the study, a convenience sample size of 54 patients is considered sufficient to evaluate whether accrual is feasible. This sample size would also provide an opportunity to estimate the CRT and SBRT 3 month complete pain relief response rates, which would provide the basis for the sample size calculation of the future randomized controlled trial. We chose a sample size that provides for standard error rates in both treatment arms to be less than 10%. Assuming that the CRT response rate is 10% to 30%, with 27 patients, the standard error for the estimated response rate will be 5.8% to 8.8%, respectively. Assuming that the SBRT response rate is about 30% to 50%, with 27 patients, the standard error for the estimated response rate would be 8.8% to 9.8%, respectively.

The trial was activated in July 2015. By November 2016, 44 patients had been enrolled onto the study and the accrual rate indicated that the sample size would be reached in 18 months, thereby meeting the primary objective of the phase II feasibility study. Other metrics of trial conduct were examined including treatment related toxicity and tolerability as well compliance with radiotherapy including quality assurance measures. No safety signals were detected in either arm. Notably, spinal fracture within the treatment fields occurred in 2 patients - both on the conventional treatment arm (CRT). Compliance with protocol mandated radiotherapy and quality assurance measures was high.

Based on the demonstration of feasibility of trial conduct and continued need to critically evaluate the efficacy of SBRT in the treatment of painful spinal metastases, approval was sought and granted in January 2017 for conversion of the study design from a randomized phase II feasibility study to a randomized phase II/III study comparing the two radiotherapy treatment strategies.

Sample size estimate for the phase III controlled trial is with a two-sided 5% level test and 80% power. Based on the results of a randomized phase II trial [*Sprave 2018*] with similar enrollment and radiobiology criteria as the current study, we estimate the complete pain responses will be 20% for the CRT and 40% for the SBRT treatment arms, respectively.

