14.6 Secondary Endpoint and Analysis

Complete pain response in the treatment area at 6 months post-radiation. All analyses for the primary endpoint will be performed for the complete pain response at 6 months post-radiation.

AMEND #1: 2017-FEB-02; AMEND #2: 2018-APR-03; AMEND #3: 2018-OCT-31

Radiation site progression-free survival (RSS PFS) is defined as the time from the date of randomization to the date of documented local progression, as defined in Section 10.2.2; or the date of death. Patients who have not progressed or died by the cutoff date of final analysis, RSS PFS will be censored on the date of the last disease assessment. A Kaplan-Meier curve for proportions of RSS PFS in each treatment arm will be displayed. The RSS PFS rates at 3 and 6 months and their 95% confidence intervals will be estimated. The 95% confidence intervals for the medial RSS PFS will be computed using the method of Brookmeyer and Crowley. The difference in distributions of RSS PFS in the two treatment arms will be compared using the log-rank test stratified by the stratification factors at randomization except study centre. Other potential important factors that predict RSS PFS will be assessed using Cox regression. Overall survival will be analysed similarly.

The incidence of acute severe adverse incidences for each arm will be calculated with its 95% confidence interval, and the analyses will be performed in a tiered comparison, i.e., comparing the overall incidence rates between treatment arms first, then comparison of radiotherapy and disease related symptoms and compared by means of Chi-square analysis or Fisher exact test.

SINS scores will be summarized for data at baseline, 3 and 6 months evaluations. The potential prognostic effects of baseline SINS score on the complete pain response at 3 months post-radiation and the overall survival will be explored using logistic and Cox regression models respectively.

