**Table 12b: Complete pain response at 3-month after treatment (per protocol and evaluable patients)**

**Table 13: Cochran Mantel Haenszel and Logistic Regression Model for Complete response rate 3-month post treatment**

Data set: All Randomized Patients

Treatment/ Prognostic Factc	Univariate Analysis 		Multivariate Analysis 	
	Odds Ratio (95%CI)	CMH p-vlaue	Odds Ratio (95% C.I.	p-value from logisti regression
Treatment arm SBRT : CRT	**.* (**.*; **.*	0.***	**.* (**.*; **.*	0.***
Prognostic factor 1 Level 1: level 2	NC 	0.***	**.* (**.*; **.*	0.***
Prognostic factor 2 Level 1: level 2	NC	0.***	**.* (**.*; **.*	0.***
Prognostic factor 3 Level 1: level 2	NC	0.***	**.* (**.*; **.*	0.***
... ...	NC	0.***	**.* (**.*; **.*	0.***

(1) Stratified by stratification factors  
 (2) Stratified Logistic regression, all factors included  
 (3) NC = not computed  
 (4) Odds ratio of first category over second category

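### The factor models for complete pain response score an outcome in which inevaluable patients count as failures, and nothing planned beside them separates poor pain relief from death or a missing diary

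*SAP*

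**What the plan says.** **The outcome rule.** Protocol 14.2 sets it for the primary endpoint: "Patients that are inevaluable for the primary endpoint due to missing data will be considered as non-responder for the intent-to-treat analysis". SAP 2.1 places every efficacy analysis on the intention-to-treat population, and SAP 2.5.2.1 fixes the denominator: "The complete pain response rate is defined as number of patients achieved complete pain response / number of patients randomized for each treatment arm". Being evaluable requires at least one dose of radiotherapy, plus pain and opioid data at baseline and at 3 months (Protocol 10.1.1, SAP 2.5.1.1).

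**The factor models.** SAP 2.5.2.1 adds: "Logistic regression will be used to assess the relationship between complete pain response incidence and the following factors". Table 13 reports them for all randomized patients, and its multivariate column is footnoted "Stratified Logistic regression, all factors included". SAP 2.5.2.2 and 2.5.2.3 repeat the analysis for 6-month complete response (Table 15) and for overall pain response (Table 17), again on all randomized patients.

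**Their purpose.** Protocol 14.2 gives the logistic model two uses: adjusting the treatment effect, and "to explore factors that are predictive of the complete pain response". Protocol 14.6 adds a related question: "The potential prognostic effects of baseline SINS score on the complete pain response at 3 months post-radiation".

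**Analyses that relax the rule.** Protocol 14.3 lists a complete-case analysis and multiple imputation as sensitivity analyses, without mentioning the factor models. The SAP's only evaluable-patient analysis of response is Table 12b, which covers the response rate and is also restricted to the per-protocol population. Table 11 gives reasons for inevaluability by arm only.

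**The concern.** For the randomized comparison, counting inevaluable patients as non-responders is a conservative choice made in advance, and both arms are treated alike. Baseline factors are not randomized. ECOG status, primary malignancy and age may plausibly be related to dying or missing the 3-month diary. If so, a factor with no bearing on pain among assessed patients will still show an odds ratio away from 1.

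What is at stake is how the factor rows are read. A low odds ratio for ECOG 2 could be reported as radiotherapy relieving pain less well in those patients, when it might reflect only that fewer of them reached the 3-month assessment. With inevaluability shown only by arm, the planned output would not let a reader tell the two apart.

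**Working it through.** **1. The coding.** The SAP does not state it beside the model; it is an inference. The model's data set is all randomized patients, the outcome is yes/no, and the only value that the plan assigns to an inevaluable patient is non-responder.

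**2. The plan's own figures use the same rule.** Protocol 14.3: "we estimate the complete pain responses will be 20% for the CRT and 40% for the SBRT treatment arms, respectively", with 15% inevaluable.
- CRT: 0.85 × 20% = 17%. SBRT: 0.85 × 40% = 34%. Both match the stated intention-to-treat rates.
- Sample size for 17% vs 34%, two-sided 5%, 80% power, 1:1: the two-proportion formula gives 102.0 per arm before rounding. With continuity correction, (102.0/4) × [1 + √(1 + 4/(102.0 × 0.17))]² = 113.5, so 114 per arm and 228 in total. This reproduces the stated figure.

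**3. Weight of the inevaluable patients.**
- Inevaluable: 0.15 × 228 ≈ 34.
- Coded non-responders, pooling the arms: 228 × (1 − 0.255) ≈ 170.
- Share: 34/170 ≈ 20% (CRT 0.15/0.83 = 18%; SBRT 0.15/0.66 = 23%).

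About one coded failure in five would be a patient with no known pain outcome.

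**4. A factor with no relation to pain.** From the plan: 15% inevaluable overall and n = 228. Assumed: 30% response among evaluable patients at both levels (midpoint of 20% and 40%), 20% of patients in the worse level, and the split of inevaluability.

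Observed rate at a level = 0.30 × (1 − inevaluable share at that level). Odds ratio = odds in the worse level ÷ odds in the other level.

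| Inevaluable, other level vs worse level | Overall check | Observed response, other vs worse | Odds ratio |
|---|---|---|---|
| 15% vs 15% | 15% | 25.5% vs 25.5% | 1.00 |
| 13.75% vs 20% | 0.8 × 13.75 + 0.2 × 20 = 15 | 25.9% vs 24.0% | 0.90 |
| 12.5% vs 25% | 0.8 × 12.5 + 0.2 × 25 = 15 | 26.25% vs 22.5% | 0.82 |
| 10% vs 35% | 0.8 × 10 + 0.2 × 35 = 15 | 27.0% vs 19.5% | 0.65 |

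Last row in full: (0.195/0.805) ÷ (0.270/0.730) = 0.2422/0.3699 = 0.65. Among evaluable patients the odds ratio is 1.00 in every row, by construction.

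**5. Chance of a false flag.** Simulating an unadjusted single-factor chi-square test at n = 228 gives rejection rates of about 5%, 5.3%, 7% and 16% for the four rows. This is not the planned stratified multivariable model, so it indicates scale only.

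**6. Sensitivity to the assumptions.** With 25% of patients in the worse level and 25% to 40% of them inevaluable, the odds ratio runs from 0.81 to 0.56, with false flags of about 9% to 32% by a normal approximation.

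**The case against.** **The outcome is legitimate.** Treated, assessed at 3 months and pain-free is a sensible composite in palliative care, where not living long enough to benefit matters. The plan applies one definition throughout. This stands: a reader might infer that the coding is an error, but the documents show a deliberate choice. The gap is that the composite is unlabelled and nothing beside it separates its parts.

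**The plan already has a complete-case analysis.** A reader of the SAP alone might infer that the trial plans no unrestricted analysis of known outcomes. Protocol 14.3 does plan one. Neither document ties it to the factor models, so the gap there remains.

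**Evaluable-only models have their own bias.** Being evaluable is a post-randomization event, so evaluable ECOG 2 patients are a selected group. Replacing the factor rows would also put two populations into a table built around one multivariable model. This stands, and it is a reason to add a model rather than substitute one.

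**The effect may be negligible.** The documents give neither the distribution of any factor nor inevaluability by factor level. Under mild imbalance the false-flag rate is close to nominal. Even at 10% vs 35%, the 95% interval around 0.65 is roughly 0.29 to 1.46 at n = 228. This stands as a limit on the size.

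**Scope.** The coding is inferred, and for Table 17 it comes only through the SAP's instruction to repeat the complete-response analyses. SINS is less clear: SAP 2.5.1.5 requires a baseline and at least one follow-up score for the spinal instability analysis. If that rule also governs the protocol's SINS question, some early deaths are already excluded. It is likewise tempting to say that the 6-month table must be worse affected; that is plausible, but neither document gives a 6-month inevaluability figure.

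**Conclusion.** The point holds as one about interpreting exploratory output. As planned, the factor odds ratios in Tables 13, 15 and 17 describe being evaluable and in response, and the output cannot separate pain relief from death or a missing diary. For a factor unrelated to pain, the distortion runs from none, if inevaluability is equal across levels, through about 0.90 and 0.82, to about 0.65 under a strong imbalance. Those values rest on the assumed 30% response, 20% prevalence and inevaluability splits; only the 15% and the 228 come from the plan.

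A reader might infer that the treatment comparison is compromised. The documents do not support that: the stratified primary test, the non-responder rule for the arms and the sample size all stand. Nor do they show that any particular factor, ECOG included, will be distorted; they show only that the planned tables could not reveal it.

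**What to change.** 1. Keep Tables 13, 15 and 17 as planned, and add a footnote that inevaluable patients are counted as non-responders. This also puts the inferred coding on record.
2. Extend the complete-case analysis of Protocol 14.3 to these models: beside each, report the same model, treatment included, in patients evaluable at that visit, without the per-protocol restriction of Table 12b.
3. Show the percentage inevaluable at that visit for each level of each factor, for example by extending Table 11.
4. State that the two models are exploratory and are to be read together.

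The cost is a few lines of SAP text and one extra run per table, using data already collected. The added 3-month models would use about 15% fewer patients on the plan's assumption and may carry selection bias, since being evaluable is determined after randomization.

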#### **Sensitivity analyses:**

- A sensitivity analysis for the complete pain response rate will be performed with the per protocol population in evaluable patients. (table 12b)

**Subgroup analysis:** the primary analysis on primary endpoint will be performed based on patients' stratification factors at baseline, i. e. Histology (radioresistant vs. radiosensitive) And "Mass"\* on imaging (present vs. absent) (Table 14) with interaction p-value to tell if any differential treatment effect across levels of stratification factors.

#### **2.5.2.2 Complete pain response at 6-month post treatment**

The same analysis on complete response rate 3 months post treatment will be performed for the complete response rate 6 months post treatment (Table 15, 16).

#### **2.5.2.3. Response to radiation treatment**

The response to radiation treatment will be determined using the overall response rate (complete response and partial response) at 3 months assessment after radiation therapy. A table will be

provided to summary the number (percentage) of patients in each response category. All analysis performed for complete pain response will also be performed for pain response (Table 17, 18).

### **2.5.2.3 Radiation site progression-free survival (RSS PFS) at 3 and 6 months**

K-M estimate of RSS PFS distribution will be displayed by treatment arm (Figure 1), and log-rank test stratified by stratification factors of Histology (radioresistant vs. radiosensitive) and “Mass” on imaging (present vs. absent) will be used to test the difference and Cox regression model stratified by the stratification factors will be used to estimate the HR and its 95% C.I. (table 19). The 3 months and 6 months RSS PFS rate and its variance will be estimated from the K-M curves by treatment arm.

**Subgroup analysis:** RSS PFS will be performed based on patients’ stratification factors at baseline, i. e. Histology (radioresistant vs. radiosensitive) and “Mass”\* on imaging (present vs. absent) (Table 20) with interaction p-value to tell if any differential treatment effect across levels of stratification factors.

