1.2 Secondary Objectives

To assess both treatment arms with respect to:

- Complete pain response in the treatment area at 6 months post-radiation, based on the International Bone Metastases Consensus Working Party Criteria.
- Radiation site progression-free survival (RSS PFS) at 3 and 6 months, using MRI imaging.
- Spinal instability as measured by the Spinal Instability Neoplastic Score at 3 and 6 months.
- Overall survival.
- Adverse event profile, using the Common Terminology Criteria for Adverse Events version 4.0 (CTCAE v 4.0).
- Health-Related Quality of Life as measured by the EORTC QLQ-C30 and QLQ-BM22 instruments.
- Economic analysis as measured by the EuroQol EQ-5D-5L instrument.
- Radiotherapy Quality Assurance (RTQA) compliance, using prospectively-defined protocol-specified quality assurance measures.

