9.1 Evaluation During and After Protocol Treatment

Patients will be evaluated during radiotherapy as well as at 4 weeks, 3 and 6 months after the end of radiotherapy.

| Investigations | | After Treatment |
|--|---|---|
| History and Physical Exam including: | 
 Physical Exam ECOG PS | As per institutional standards, perform if clinically indicated |
| Radiology | 
 MRI entire spine | At 3 and 6 months |
| Pain / Analgesic Assessment | 
 Patient Diary* | At 4 weeks and at 3 and 6 months |
| Adverse Events** | Adverse events \geq grade 2 will be recorded and graded according to the NCI Common Terminology Criteria for Adverse Events (CTCAE) (Appendix V). | During radiotherapy treatment* and post radiotherapy at 4 weeks and at 3 and 6 months |
| Health-Related Quality of Life*** | 
 EORTC QLQ-C30 and QLQ-BM22 questionnaires | At 4 weeks and at 3 and 6 months |
| Economic Analysis**** | 
 EQ-5D-5L questionnaire | At 4 weeks and at 3 and 6 months |
| Other Assessments | 
 SINS score (use scoring sheet**) | At 3 and 6 months |
| Correlative Studies*** | 
 Optional, for consenting patients only: Plasma and Serum | Immediately after the second fraction of protocol therapy |
| 
* See Appendix VII. Worst Pain to be recorded only for the site included in the radiotherapy target volume. The diary MUST capture all medications that affect pain directly (e.g. opioids, non-opioid analgesics) or indirectly (e.g. steroids, co-analgesics) as well as any pre-medications given for the protocol radiotherapy treatment. Other medications may also be listed. Site staff may assist the patient with listing medication names /routes on the diary.
 
** Report only Adverse Events \geq grade 2, using the CTCAE v 4.0. See Appendix V.
 
*** The Quality of Life and Economic Analysis questionnaires will be completed by the patient electronically. See Appendix VI.
 
* Adverse events experienced by the patient during / shortly after radiotherapy treatment, including whether the patient experienced pain exacerbation (Pain Flare) at the treated site, must be evaluated.
 
** See Appendix III.
 
*** See Section 13 and the SC.24 Specimen Collection Manual that is posted on the trial webpage.
 | | |

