10.1.2 Evaluable for Radiation Site Progression Free Survival (RSS PFS)

All patients who have received at least one dose of radiotherapy and have an MRI of entire spine at baseline and at least the 3 month follow up contact will be considered evaluable for RSS PFS. Patients will have RSS PFS assessed as described below in Section 10.2.3.

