APPENDIX I - PATIENT EVALUATION FLOW SHEET

| Required Investigations | Prior to Randomization | After randomization and prior to 1st fraction of RT | Day 0* | Immediately after 2nd fraction of RT | During RT treatment | 4 wks post-RT | 3 months post-RT | 6 months post-RT |
|--|------------------------|---|--------|--------------------------------------|---------------------|--|------------------|------------------|
| History and Physical | | | | | | | | |
| Physical Exam | ≤ 4 weeks | | | | | As per institutional standards – perform if clinically indicated | | |
| ECOG Performance Status | ≤ 4 weeks | | | | | | | |
| Radiology | | | | | | | | |
| MRI entire Spine | ≤ 8 weeks | | | | | | X | X |
| Pain / Analgesic Assessment | | | | | | | | |
| Patient Diary | ≤ 7 days | | X | | | X | X | X |
| Adverse Events | | | | | | | | |
| Baseline Symptoms / Adverse Events** | ≤ 7 days | | | | X* | X | X | X |
| Health-Related Quality of Life and Economic Analysis | | | | | | | | |
| EORTC QLQ-C30 and QLQ-BM22 questionnaires | ≤ 7 days | | X | | | X | X | X |
| EQ-5D-5L questionnaire | | | | | | | | |
| Other Assessments | | | | | | | | |
| SINS score*** | ≤ 7 days | | | | | | X | X |
| Pregnancy Test | ≤ 7 days | | | | | | | |
| Correlative Studies | | | | | | | | |
| Serum and Plasma Collection** | | X | | X | | | | |
| 
* Day 0 is defined as the day of the first fraction of radiotherapy, but prior to the administration of radiotherapy
 
** Report only Adverse Events ≥ grade 2, using the CTCAE v 4.0. See Appendix V.
 
*** See SINS scoring sheet on Appendix III
 
♦ Evaluation of adverse events experienced by the patient during / shortly after radiotherapy treatment, including whether the patient experienced pain exacerbation (Pain Flare) at the treated site
 
♦♦ See section 13 and the SC.24 Specimen Collection Manual posted on the SC.24 trial webpage.
 | | | | | | | | |

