### **2.5.1.4 Radiation site progression-free survival (RSS PFS) at 3 and 6 months**

Radiation site progression free survival is defined as the time from randomization to local progression or death. For patients who did not reported progression of disease and alive will be censored at the last disease evaluation time. It is based on the center investigator reported data.

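### The 3- and 6-month RSS PFS rates are read from a curve timed from randomization, but the MRIs fall 3 and 6 months after radiotherapy ends, so each rate misses its own on-schedule scan

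*SAP*

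**What the plan says.** **Time origin.** SAP 2.5.1.4: "Radiation site progression free survival is defined as the time from randomization to local progression or death". Protocol 10.2.2 and 14.6 use the same origin, and 14.6 dates progression when it is documented.

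**Censoring.** SAP 2.5.1.4: "For patients who did not reported progression of disease and alive will be censored at the last disease evaluation time".

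**Rates.** SAP 2.5.2.3: "The 3 months and 6 months RSS PFS rate and its variance will be estimated from the K-M curves by treatment arm". Protocol 14.6: "The RSS PFS rates at 3 and 6 months and their 95% confidence intervals will be estimated".

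**Scan schedule.** Protocol 9.1: "Patients will be evaluated during radiotherapy as well as at 4 weeks, 3 and 6 months after the end of radiotherapy". The table there places the whole-spine MRI at the 3- and 6-month visits only, and the column heads in Appendix I agree: "4 wks post-RT | 3 months post-RT | 6 months post-RT".

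**Role of the MRI.** The objective in Protocol 1.2 is "Radiation site progression-free survival (RSS PFS) at 3 and 6 months, using MRI imaging". Protocol 10.1.2 requires that patients "have an MRI of entire spine at baseline and at least the 3 month follow up contact will be considered evaluable for RSS PFS".

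Neither document gives an MRI window, a rule assigning scans to nominal visits, a later reading point or an interval-censored method for RSS PFS. The SAP sets visit windows only for quality of life (2.9.2.1). It tabulates the time from randomization to radiotherapy (Table 25a) but does not use it for RSS PFS.

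**The concern.** Progression that is first seen on a scan enters the Kaplan-Meier curve on the scan date. If the curve is read at 3 months from randomization and the scan is due 3 months after the last fraction, the reading comes before the scan. A lesion first seen on a punctual 3-month MRI then cannot lower the 3-month rate, although that MRI is how the protocol intends to measure the endpoint. The same happens at 6 months with the second scan.

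RSS PFS at 3 and 6 months is a named secondary endpoint, and both rates are promised with confidence intervals. A reader would take the 3-month figure as MRI-based local control. As specified it is close to overall survival, and it can look alike in two arms whose local control differs.

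**Working it through.** **1. Plan's own figures.** The documents give no rate, event count or power for RSS PFS, so there is nothing to reproduce for this endpoint. The one design figure is N = 228. A two-proportion calculation with 17% against 34%, two-sided 5% and 80% power gives 102.0 per arm, or 113.5 with continuity correction, hence 114 per arm and 228 in total. It is used below only for scale.

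**2. Scan dates.** Inputs: start of radiotherapy 0 to 21 days after randomization (Protocol 8.0); CRT in 5 daily fractions and SBRT in 2 (Protocol 8.1.1); SBRT completed within 10 days (Protocol 8.3.5.4). Scan day = days to start + days from first to last fraction + 91.3 or 182.6.

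| | Last fraction, days after randomization | First scan (rate read at day 91.3) | Second scan (rate read at day 182.6) |
|---|---|---|---|
| CRT | 4 to 27 (4 days, or 6 across a weekend) | 95.3 to 118.3 | 186.6 to 209.6 |
| SBRT, consecutive days | 1 to 22 | 92.3 to 113.3 | 183.6 to 204.6 |
| SBRT, full 10 days | up to 30 | up to 121.3 | up to 212.6 |

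Every on-schedule scan falls about 1 to 30 days after the point at which its rate is read. This step uses only the documents' dates.

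**3. Size at 3 months.** Assumptions: 20% mortality at 6 months with constant hazard; deaths independent of progression; 1-year local control L of 45%, 60% or 80%; scans complete and on schedule; progression found only at scans. Protocol 2.1 gives about 45% at one year, for bulky tumours. Protocol 2.2 gives about 80% for SBRT without a time point. The 60% and the mortality are not document figures. Let k be the Weibull shape of time to progression (k = 1 is constant hazard).

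- Planned reading = survival at 3 months = 0.80^0.5 = 0.894, whatever L is.
- True RSS PFS = 0.894 × L^(0.25^k).
- Error = 0.894 × (1 − L^(0.25^k)).

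| k | L = 45% | L = 60% | L = 80% |
|---|---|---|---|
| 1 | 0.894 − 0.733 = +16.2 | 0.894 − 0.787 = +10.7 | 0.894 − 0.846 = +4.9 |
| 1.5 | 0.894 − 0.809 = +8.5 | 0.894 − 0.839 = +5.5 | 0.894 − 0.870 = +2.5 |
| 2 | 0.894 − 0.851 = +4.4 | 0.894 − 0.866 = +2.8 | 0.894 − 0.882 = +1.2 |

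Errors are in percentage points. In each row the planned reading is the same for all three levels of local control.

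**4. Size at 6 months, same assumptions.** By day 182.6 only first-scan progression has been counted. The reading is therefore 0.80 × L^(s^k), with s the first-scan time in years, averaged over its range. The true value is 0.80 × L^(0.5^k).

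- k = 1: readings 0.633, 0.689 and 0.749 against 0.537, 0.620 and 0.716, errors +9.7, +6.9 and +3.4.
- k = 1.5: +10.2, +7.0 and +3.3.
- k = 2: +9.2, +6.2 and +2.8.

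**5. Early scans, clinical detection and missed scans.** Simulation with constant hazard and 200,000 patients per arm covered 144 combinations: mortality 20% or 30%; L of 45%, 60% or 80%; scans on schedule or scattered by ±14 or ±28 days; none or 30% of progressions found at onset; 3-/6-month scans missed at random in 0/0, 15/15, 15/25 or 20/40%.

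- 3-month error: +1.7 to +16.3, positive in all 144.
- 6-month error: −4.5 to +10.0. With complete scans it was +1.2 to +9.7. It was zero or negative in 29 combinations, all with missed scans, 21 of them at L = 80%.
- Example on schedule at 20% mortality with 20/40% missed: 6-month error +6.1 at L = 45% and −1.0 at L = 80%.

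The reversal comes from the censoring rule. Living patients leave the risk set at their last scan, while later deaths still count. With rising hazard, missed scans and scattered scans together, the 3-month error fell to as little as +0.2.

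**6. Scale.** With 114 per arm the standard error of a rate is √(0.89 × 0.11/114) = 2.9 points to √(0.54 × 0.46/114) = 4.7 points.

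**The case against.** Timing PFS from randomization and dating progression when it is documented are standard practice. So is reading a Kaplan-Meier curve at a round time. No between-arm test of these rates is planned, and a footnote on scan timing would disclose the issue. This stands in part: neither the time origin nor the event definition is at fault, and the matter is confined to two reported rates. A footnote would not, however, restore the missing scan results.

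The 3-month size rests heavily on a constant hazard from randomization. This stands. At shape 2 the error is roughly the size of one standard error or less, so +16 should not be quoted alone. The inputs are also weak, as noted above.

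The simulation lets SBRT finish as late as day 31, whereas two daily fractions imply about day 22. More SBRT scans then fall on or before the landmark under ±28-day scatter (about 29% rather than 22–23%). The error changes little, from +3.9 to +3.6 points.

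Three stronger readings are tempting, and the documents support none of them:

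- **That the treatment comparison is invalid.** The stratified log-rank test and Cox hazard ratio do not depend on where the curve is read. Their sensitivity to small arm differences in scan timing has not been fully checked, however. One limited simulation (3-day gap, 25% mortality, no missed scans, 2,000 replicates) gave type I error of 5.0% to 7.0%, with a Monte Carlo standard error near 0.5 point. That neither clears the test nor condemns it.
- **That the 6-month rate is always too high.** It is not when many scans are missed.
- **That the primary endpoint or N = 228 is affected.** Pain response is defined post-radiation, and the sample size does not use RSS PFS.

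**Conclusion.** The concern holds for the reported landmark rates. The mismatch follows from the documents' own dates and nothing in either document corrects it. At 3 months the rate is too high in both arms and obscures differences in local control. The direction was upward in every case run, provided that some local progression occurs by then and is found mainly on the scheduled MRI. The size runs from about +16, +11 and +5 points (local control 45%, 60%, 80%; constant hazard) to +4, +3 and +1 (shape 2), and less when scans are missed and scattered. At 6 months the error is about +10, +7 and +3 with complete scans and depends little on hazard shape, but it can vanish or reverse with many missed scans. All these sizes rest on assumed mortality, progression and detection. The point should be fixed, but it is no threat to the trial's main conclusion.

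**What to change.** Change SAP 2.5.2.3 to say, in substance:

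- RSS PFS rates are reported at the 3- and 6-month post-radiotherapy visits.
- A scheduled MRI is assigned to its nominal visit if it falls within a stated window around 3 or 6 months after the end of radiotherapy. A window of ±4 weeks would match the width used at 3 and 6 months in SAP 2.9.2.1, but that section labels its times from the start of radiotherapy, so the anchor must be stated afresh.
- Deaths and progression found between visits count when they occur.
- A living patient with no scan in the window is censored at that visit, just before its scan results are counted.
- All randomized patients are included, with visits set from randomization for those not irradiated.
- The number without a scan at each visit is reported by arm, with the statement that the method assumes scans are missed at random.

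Keep Figure 1, the stratified log-rank test and the Cox model from randomization.

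The missed-scan rule is needed. In the 144 combinations, visit assignment with censoring left at the last scan gave 6-month errors of −7.3 to +0.8 points. With the rule, both rates were within 1.2 points of true status at the visit. That result assumes a constant hazard and scans missed at random; informative missingness was not examined.

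**Cost.** A SAP wording change and minor programming, with no new data, since scan, radiotherapy and death dates are already collected. The rates would refer to a slightly later time: under constant hazard, the true values for 45% against 80% local control become 0.69 against 0.82 at 3 months and 0.51 against 0.70 at 6 months, instead of 0.73 against 0.85 and 0.54 against 0.72. They would not be readable from Figure 1, and scans or deaths after a missed visit would not be used.
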